7.4 Reporting of serious adverse events

All SAEs have to be reported whether or not considered causally related to the IP or to the study procedure(s). All SAEs will be recorded in the eCRF and submitted as described in each arm.

If any SAE occurs in the course of the study, then Investigators or other site personnel will inform the appropriate AstraZeneca representatives within 1 day (ie, immediately but **no later than 24 hours** of when he or she becomes aware of it).

The designated AstraZeneca representative will work with the Investigator to ensure that all the necessary information is provided to the AstraZeneca Patient Safety data entry site **within**

1 calendar day of initial receipt for fatal and life-threatening events **and within 5 calendar days** of initial receipt for all other SAEs.

For fatal or life-threatening AEs where important or relevant information is missing, active follow-up is undertaken immediately. Investigators or other site personnel will inform AstraZeneca representatives of any follow-up information on a previously reported SAE within 1 calendar day (ie, immediately but **no later than 24 hours** of when he or she becomes aware of it).

Please refer to the arm-specific Safety Reporting Guidelines. The AstraZeneca representative will advise the Investigator/study site personnel how to proceed. AstraZeneca or their representative will provide regulatory authorities, Ethics Committees (ECs), and Principal Investigators with clinical safety updates/reports according to local requirements.

The Principal Investigator is responsible for ensuring that procedures and expertise are available to handle medical emergencies during the study. **A medical emergency usually constitutes an SAE and is to be reported as such.**

7.5 Adverse events of special interest

An adverse event of special interest (AESI) is one of scientific and medical interest specific to the understanding of the study treatment and may require close monitoring and rapid communication by the Investigator to the Sponsor. An AESI may be serious or non-serious. The rapid reporting of AESIs allows ongoing surveillance of these events in order to characterize and understand them in association with the use of the individual investigational products.

Please see the relevant arm appendix for applicable AESIs.

7.6 Overdose

Use of any agent studied in doses in excess of that specified in the protocol or arms is considered to be an overdose. There is currently no specific treatment in the event of overdose of any of these agents, and possible symptoms of overdose are not established.

- An overdose with associated AEs is recorded as the AE diagnosis/symptoms on the relevant AE arms in the eCRF and on the Overdose eCRF for that arm.
- An overdose without associated symptoms is only reported on the Overdose eCRF for that arm.

If an overdose on an AstraZeneca study drug occurs in the course of the study, then Investigators or other site personnel should inform appropriate AstraZeneca representatives immediately, or **no later than 24 hours** of when he or she becomes aware of it.

The designated AstraZeneca representative will work with the Investigator to ensure that all relevant information is provided to the AstraZeneca Patient Safety data entry site.

For overdoses associated with an SAE, the standard reporting timelines apply; see Section 7.4. For other overdoses, reporting must occur within 30 days.

7.7 Pregnancy

All pregnancies and outcomes of pregnancy should be reported to AstraZeneca except for:

Pregnancy discovered before the study patient has received any study drugs.

7.7.1 Maternal exposure

If a patient becomes pregnant during the course of the study, the study treatment should be discontinued immediately.

Pregnancy itself is not regarded as an AE unless there is a suspicion that the study treatment under study may have interfered with the effectiveness of a contraceptive medication. Congenital abnormalities/birth defects and spontaneous miscarriages should be reported and handled as SAEs. Elective abortions without complications should not be handled as AEs. The outcome of all pregnancies (spontaneous miscarriage, elective termination, ectopic pregnancy, normal birth, or congenital abnormality) should be followed up and documented even if the patient was discontinued from the study.

If any pregnancy occurs in the course of the study, then the Investigator or other site personnel informs the appropriate AstraZeneca representatives within 1 day (ie, immediately **but no later than 24 hours** of when he or she becomes aware of it).

The designated AstraZeneca representative works with the Investigator to ensure that all relevant information is provided to the AstraZeneca Patient Safety data entry site within 1 to 5 calendar days for SAEs (see Section 7.4) and within 30 days for all other pregnancies.

The same timelines apply when information on the outcome of the pregnancy is available.

The PREGREP arm in the eCRF is used to report the pregnancy, and the PREGOUT is used to report the outcome of the pregnancy.

7.7.2 Paternal exposure

Please see specific arm for the required time for male patients to refrain from fathering a child, donating sperm during the study, or details of reporting outcomes of all pregnancies (spontaneous miscarriage, elective termination, ectopic pregnancy, normal birth, or congenital abnormality) occurring from the date of the first dose of study medication.

Where a report of pregnancy is received, prior to obtaining information about the pregnancy, the Investigator must obtain the consent of the patient's partner. Therefore, the local study team should adopt the generic informed consent form (ICF) template in line with local procedures and submit it to the relevant ECs/Institutional Review Boards (IRBs) prior to use.

7.8 Management of investigational product-related toxicities

Please refer to the relevant section (eg, Section 7.5 for Arm A) for specific toxicity management guidelines applicable to each arm of the study.

All toxicities will be graded according to NCI CTCAE version 4.03 (see study-specific sub-protocols).

7.9 Study governance and oversight

A Review Committee, which includes the Principal Investigator, the AstraZeneca Study Physician, and statisticians, will convene after the first 10 patients are enrolled onto each arm to assess whether the arm should continue to accrue or stop recruitment based on an interim analysis including ORR (see section 9.5.7). The recommendation of the Review Committee will be discussed at a clinical project level before endorsement.

If the decision is made to open stage 2 of a particular arm the Review Committee will review the results of the primary analysis for the first 20 subjects after completion of 12 weeks follow up. Based on the totality of the data and the benefit-risk assessment the Review Committee may recommend expansion of that arm. The recommendation of the Review Committee will be discussed at a clinical project level before endorsement.

No Steering Committee and/or Scientific Advisory Committee will be used in this study. There is an internal AstraZeneca BALTIC Study Team to oversee the global operational and medical monitoring aspects of the study. The safety of all subjects in the BALTIC study is closely monitored on an ongoing basis by this team in consultation with AstraZeneca Patient Safety and clinical teams responsible for the individual products under investigation in each arm. Issues identified will be addressed; for instance, this could involve amendments to the study protocol and letters to Investigators.

8. INVESTIGATIONAL PRODUCT AND OTHER TREATMENTS

8.1 Identity of investigational product(s)

Please refer to the relevant appendix (eg, [Appendix A](#) for Arm A) for specific IP information applicable to each arm of the study.

8.1.1 Duration of treatment

Unless specific treatment discontinuation criteria are met, all patients will continue therapy until disease progression.

8.1.2 Follow up of patients post discontinuation of study drug

Please refer to the relevant appendix (eg, [Appendix A](#) for Arm A) for specific information applicable to each arm of the study.

8.2 Dose and treatment regimens

Please refer to the relevant arm appendix (eg, [Appendix A](#) for Arm A) for specific dose and treatment regimens.

8.3 Labeling

Labels will be prepared in accordance with Good Manufacturing Practice (GMP) and local regulatory guidelines. The labels will fulfil GMP Annex 13 and regulatory requirements of each country participating in the study. The labels will be translated into local languages where applicable as required by local regulations. Labels will be provided as either singlepanel labels or as multi-language booklet labels.

The patient emergency contact details and patients' dosing instructions will not be on the labels but can be found in the informed consent and the "Patient Information Card." For emergency purposes, the patient must be in possession of the emergency contact details at all times.

Please see the relevant arm appendix (eg, [Appendix A](#) for Arm A) for specific labeling information.

8.4 Storage

All study medications should be kept in a secure place under appropriate storage conditions. The IP label on the pack/bottle/carton will specify the appropriate storage. Storage is also described in the IB of each product and in the IP Handling Instruction

8.5 Compliance

The administration of all study drugs (including IPs) should be recorded in the appropriate sections of the CRF.

8.6 Accountability

The study drug provided for this study will be used only as directed in the study protocol.

Study site personnel will account for all study drugs received at the site, unused study drugs, and study drugs for appropriate destruction. Certificates of delivery, destruction, and/or return should be signed.

8.7 Concomitant and other treatments

The Investigator must be informed as soon as possible about any medication taken from the time of screening until the end of the clinical treatment phase of the study including the follow-up period following the last dose of treatment. Any concomitant medication(s), including herbal preparations, taken during this time will be recorded in the eCRF.

Patients must be instructed not to take any medications, including over-the-counter products, without first consulting with the Investigator.

Restricted, prohibited, and permitted concomitant medications are described in the relevant arm appendix.

8.7.1 Other concomitant treatment

Other medication other than that described above, which is considered necessary for the patient’s safety and well-being, may be given at the discretion of the Investigator and recorded in the appropriate sections of the CRF.

8.8 Post-study access to study treatment

Patients are permitted to receive study treatment until confirmed progression. AstraZeneca may continue to provide open-label drugs to patient, if such becomes available.

After discontinuation of study treatment, the Investigator will be at liberty to define further most appropriate anti-cancer treatment.

9. STATISTICAL ANALYSES BY ASTRAZENECA

9.1 Statistical considerations

All statistical analyses will be performed by AstraZeneca or its representatives. The analyses will be descriptive, and no inferential analysis will be performed based on statistical tests.

A comprehensive statistical analysis plan (SAP) will be prepared and finalized within 3 months of enrollment of the first patient, and any subsequent amendments will be documented, with final amendments completed prior to reporting of the data.

9.2 Sample size estimate

This study will enroll up to 40 eligible patients in each treatment arm. Stage 1 will initially enroll a minimum of 10 patients; after a minimum of 12 weeks an interim analysis will be performed, which will determine whether recruitment should expand to the second stage (an additional 10 patients for a total of 20 eligible patients) or stop. If the results of the primary ORR from the completed 2nd stage are encouraging the Review Committee could recommend expansion to add up to an additional 20 eligible subjects (for a total of 40 eligible patients), to further explore the findings.

The table below shows the 2-sided exact 95% confidence intervals (CI) for the ORR of a treatment arm at each stage of the study, assuming the observed ORR is **cci**% or **cci**%:

ORR	cci %	CCI
Stage 1 (10 patients)	(cci %, cci %)	(cci %, cci %)
Stage 2 (20 patients in total)	(cci %, cci %)	(cci %, cci %)

ORR	CCI%	CCI%
Expansion (40 patients in total)	(CCI%, CCI%)	(CCI%, CCI%)

9.3 Definitions of analysis sets

Definitions of the analysis sets for each outcome variable are provided in Table 1.

Table 1 Summary of outcome variables and analysis populations

Outcome variable	Population
Efficacy data	
ORR, DoR, DCR, TTR, PFS and OS	Full Analysis Set
Demography	Full Analysis Set
PK data	PK Analysis Set
Safety data	
Exposure	Full Analysis Set
AEs	Full Analysis Set
Laboratory measurements	Full Analysis Set
Vital signs	Full Analysis Set
ECGs	Full Analysis Set

AE Adverse Event; DCR Disease control rate; DoR Duration of response; ECG Electrocardiogram;
ORR Objective response rate; OS Overall survival; PFS Progression-free survival; PK Pharmacokinetic;
TTR Time to response.

9.3.1 Full Analysis Set

The Full Analysis Set (FAS) will include all treated patients. Patients who were enrolled but did not subsequently go on to receive IP are not included in the FAS.

9.3.2 PK Analysis Set

All patients who received at least 1 dose of study treatment per the protocol for whom any post-dose data are available and who do not violate or deviate from the protocol in ways that would significantly affect the PK analyses will be included in the PK Analysis Set. The population will be defined by the Study Physician, Pharmacokineticist, and Statistician prior to any analyses being performed.

9.4 Outcome measures for analyses

9.4.1 Calculation or derivation of efficacy variables

The analysis of the primary endpoint, ORR, and the analyses of the secondary endpoints, DoR, DCR, TTR, and PFS, will be based on site Investigator assessment using RECIST 1.1. In addition, OS will also be evaluated.

9.4.1.1 RECIST 1.1-based endpoints

Investigator RECIST 1.1-based assessments

All RECIST 1.1 assessments, whether scheduled or unscheduled, will be included in the calculations. This is also regardless of whether a patient discontinues study treatment or receives another anticancer therapy.

At each visit, patients will be programmatically assigned a RECIST 1.1 visit response of CR, PR, SD, or PD depending on the status of their disease compared with baseline and previous assessments. Baseline will be assessed within the 28 days prior to enrollment. If a patient has had a tumor assessment that cannot be evaluated, then the patient will be assigned a visit response of NE (unless there is evidence of progression, in which case the response will be assigned as PD).

Please refer to [Appendix F](#) for the definitions of CR, PR, SD, and PD.

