6.1 Efficacy assessments

This study will evaluate the primary endpoint of ORR as determined by Investigator assessment according to RECIST 1.1 criteria. Efficacy assessments of PFS, TTR, DoR, and DCR will be derived (by AstraZeneca) using Investigator RECIST 1.1 assessments. In addition, OS will be determined as a secondary efficacy endpoint.

Tumor assessments use images from CT (preferred) or MRI, each preferably with IV contrast, of the chest, abdomen, and pelvis, collected during screening/baseline and at regular (follow-up) intervals during study treatment. Any other areas of disease involvement should be additionally imaged based on the signs and symptoms of individual patients.

The RECIST 1.1 guidelines ([Appendix F](#)) provide a method of assessment of change in tumor burden in response to treatment. Screening/Baseline imaging should be performed no more than 28 days before start of study treatment and ideally should be performed as close as possible to and prior to the start of study treatment. The RECIST 1.1 assessments of baseline images identify target (defined and measurable) and non-target lesions. Each lesion (and any new lesion) is evaluated in subsequent on-treatment follow-up images. This allows determination of follow-up target lesion response, non-target lesion response, and overall timepoint tumor responses (CR, PR, SD, PD, or not evaluable [NE]).

Efficacy for all patients (all arms) will be assessed on images collected either every 6 or 8 weeks \pm 1 week until confirmed objective disease progression or when the patient has been taken off-study. It is important to follow the assessment schedule as closely as possible (refer to the study plans in each arm [screening and treatment period, and follow-up]). If an unscheduled imaging assessment is performed and the patient has not progressed, every attempt should be made to perform the subsequent assessments at his or her next regularly scheduled imaging visit.

According to RECIST 1.1, objective tumor response (CR or PR) should be confirmed preferably at the next scheduled imaging visit and not less than 4 weeks after the visit when the response was last observed.

Patients who have discontinued treatment due to toxicity or symptomatic deterioration, clinical progression, or who have commenced subsequent anticancer therapy will be followed up with tumor assessments until RECIST 1.1-defined PD or until death (whichever comes first) and followed for survival.

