For the immunotherapy arm only, a follow-up scan is requested following an overall timepoint assessment of progression by RECIST 1.1, preferably at the next scheduled imaging visit and no earlier than 4 weeks after the previous assessment of PD in the absence of clinically significant deterioration. Treatment will continue between the initial assessment of

progression and confirmation for progression. If a patient discontinues treatment (and/or receives a subsequent anticancer therapy) after the initial assessment of progression, then the patient should continue to be followed with scheduled imaging until confirmed objective disease progression.

It is important to follow the assessment schedule as closely as possible. Please refer to the study plan of the relevant arm appendix.

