9.4.1.2 Primary endpoint (objective response rate)

ORR (per RECIST 1.1 as assessed by the site Investigator) is defined as the number (%) of patients with a confirmed objective response of CR or PR and will be based on patients in the evaluable set.

A confirmed response of CR/PR means that a response of CR/PR is recorded at 1 visit and confirmed by repeat imaging not less than 4 weeks after the visit when the response was first observed with no evidence of progression between the initial and CR/PR confirmation visit. Therefore, data obtained up until progression, or the last evaluable assessment in the absence of progression, will be included in the assessment of ORR. Any patient who discontinues treatment without progression, receives a subsequent therapy, and then responds will not be included as responders in the ORR.

For sensitivity analysis, ORR may be assessed using the RECIST 1.1 site Investigator tumor data following a modification where any objective progression requires confirmation. Therefore, data obtained up until confirmed progression, or the last evaluable assessment in the absence of a confirmed progression, may be included in the assessment of ORR. Note that the response may be after an unconfirmed progression.

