9.4.1.3 Secondary endpoints

Secondary efficacy variables include DoR, DCR, TTR, PFS, and OS. Efficacy data will be summarized and analyzed based on the FAS.

Duration of response

DoR (per RECIST 1.1 as assessed by the site Investigator) will be defined as the time from the date of first documented response (which is subsequently confirmed) until the first date of documented progression or death in the absence of disease progression. The end of response should coincide with the date of progression or death from any cause used for the RECIST 1.1 PFS endpoint.

The time of the initial response will be defined as the latest of the dates contributing toward the first visit response of CR or PR. If a patient does not progress following a response, then their DoR will be censored at the PFS censoring time. DoR will not be defined for those patients who do not have documented response (which is subsequently confirmed).

Sensitivity analyses of DoR may be performed based on Investigator assessment according to RECIST 1.1 modified for confirmation of progression.

Disease control rate

DCR at 12 weeks is defined as the percentage of patients who have a best objective response of CR or PR in the first 13 weeks (to allow for a late assessment within the assessment window) or who have demonstrated SD for a minimum interval of 11 weeks (to allow for an early assessment within the assessment window) following the start of study treatment.

DCR will be determined programmatically based on RECIST 1.1 using site Investigator data and all data up until the first progression event.

Sensitivity analyses of DCR may be performed based on Investigator assessment according to RECIST 1.1 modified for confirmation of progression.

Time to response

TTR (per RECIST 1.1 as assessed by the Investigator) is defined as the time from the date of first dose until the first date of documented response (which is subsequently confirmed). The date of first documented response should coincide with that used for the RECIST 1.1 DoR endpoint. TTR will not be defined for those patients who do not have documented response (which is subsequently confirmed).

Progression-free survival

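### DCR counts scans taken after a switch to another anticancer drug, although ORR excludes a response that begins there; the ORR exclusion itself is unclear in two cases

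*Protocol*

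**What the plan says.** Section 9.4.1.1 of the protocol sets one rule for all RECIST-based endpoints. Every scheduled or unscheduled assessment is used, and "This is also regardless of whether a patient discontinues study treatment or receives another anticancer therapy".

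Section 6.1 ensures that such scans exist. Patients "who have commenced subsequent anticancer therapy will be followed up with tumor assessments until RECIST 1.1-defined PD". For the immunotherapy arm, imaging also goes on until progression is confirmed in this case: "If a patient discontinues treatment (and/or receives a subsequent anticancer therapy) after the initial assessment of progression".

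Section 9.4.1.2 contains the only exception, and it is written for ORR: "Any patient who discontinues treatment without progression, receives a subsequent therapy, and then responds will not be included as responders in the ORR". A response there counts as confirmed if it is "confirmed by repeat imaging not less than 4 weeks after the visit when the response was first observed with no evidence of progression". For the sensitivity ORR, in which progression must itself be confirmed, the section adds: "Note that the response may be after an unconfirmed progression".

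Section 9.4.1.3 defines DCR at 12 weeks as CR or PR within 13 weeks, or SD lasting at least 11 weeks. The data cut is: "DCR will be determined programmatically based on RECIST 1.1 using site Investigator data and all data up until the first progression event". Subsequent therapy is not mentioned. For PFS the same section says expressly that later therapy is ignored, and DoR takes its end date from PFS.

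**The concern.** DCR is meant to describe what the study combination does in the first 12 weeks. As written, tumour control seen while the patient is on a different drug is credited to the study arm. The protocol also treats one and the same PR in two ways: as another drug's effect for ORR, and as the study drug's effect for DCR.

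Each arm is single-arm, with at most 40 patients and no concurrent control in which similar misattribution would partly cancel. Sections 2.2.1 and 7.9 base decisions to open stage 2 or to expand on the totality of the data, so DCR can influence them even though it is secondary.

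The protocol accepts the principle for safety. Section 9.4.2.1 cuts the AE summary tables at the first subsequent therapy, to avoid attributing a later drug's effects to the study drug, and gives the uncut version as a separate summary. DCR has only the uncut version.

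**Working it through.** The protocol prints no figure that depends on this rule, and the target rates and intervals in section 9.2 are redacted, so there is nothing to reproduce. The check is a reading of the definitions, followed by the weight of one patient.

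**1. One patient traced through the rules.** Assume a patient in Arm A or C, where scans fall at weeks 8 and 12. The patient stops for toxicity at week 3 without progression and starts another drug at week 5 (weeks 3 and 5 are illustrative).

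| Finding at week 12, on the other drug | ORR (9.4.1.2) | DCR (9.4.1.3) |
|---|---|---|
| First PR, later confirmed | Not a responder: stopped without progression, switched, then responded | Controlled: PR, 12 ≤ 13 weeks, no progression before it |
| SD | Not a responder | Controlled: SD, 12 ≥ 11 weeks, no progression before it |

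No other section removes this patient from the DCR numerator.

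**2. Direction.** Compare with a rule that uses only scans before the switch and counts a patient who switches before meeting the criterion as not controlled. Patients who met the criterion before switching are controlled under both rules. Patients who progress after switching without having met it are not controlled under either. The rules differ only for patients who first meet the criterion after switching, and the current rule counts all of them as controlled. The difference can therefore only raise DCR.

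**3. Size per patient.** The weight of one patient is 100/n points: 100/10 = 10, 100/20 = 5, 100/40 = 2.5. Exact (Clopper-Pearson) 95% intervals for assumed counts:

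| n | As counted | One removed | Two removed |
|---|---|---|---|
| 20 | 8/20 = 40% (19.1 to 63.9) | 7/20 = 35% (15.4 to 59.2) | 6/20 = 30% (11.9 to 54.3) |
| 40 | 16/40 = 40% (24.9 to 56.7) | 15/40 = 37.5% (22.7 to 54.2) | 14/40 = 35% (20.6 to 51.7) |

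The counts only show scale. The protocol gives no basis for the number of patients affected.

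**4. Where the ORR exception is unclear.**

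(a) Confirmation. A first PR is seen on study drug, the patient switches, and the repeat scan at least 4 weeks later is taken on the next drug. The conditions for confirmation in 9.4.1.2 are met. The exception describes a patient who switches and responds afterwards; read literally, this patient responded beforehand. The response would enter ORR, and with it TTR and DoR.

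(b) Modified-RECIST ORR. A patient stops after a first, unconfirmed PD, switches and then responds. Section 6.1 keeps scanning this patient, and 9.4.1.2 lets a response follow an unconfirmed progression. The exception covers only patients who stopped without progression; read literally, this patient did not. Section 9.4.1.2 says this analysis may be done; section 9.5.2 says it will be.

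**The case against.** The case against is strong on everything except DCR.

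**Primary ORR.** A reader might infer that responses to a later drug inflate the primary endpoint and could carry an arm past the interim examples in section 2.2.1 (0/10 for stopping, at least 3/10 for promising efficacy). The text does not support that. A response that begins on later therapy is already excluded from ORR, so only the confirmation case could add a responder. That case is narrow: in Arms A and C a week-8 PR is due for confirmation at week 12, and the shrinkage arose on study drug. The exception can also be read as referring to a confirmed response, which would exclude the patient.

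**Modified-RECIST ORR.** If progression must be confirmed in this analysis, an unconfirmed PD is arguably not yet progression, and the exception would then apply. This is also a sensitivity analysis. The objection stands this far: cases (a) and (b) are ambiguities, not demonstrated errors. A programmed derivation still needs one stated reading.

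**Retreatment.** A reader might add Arm A retreatment to the list. It does not belong there. It is the same protocol regimen. Data after a confirmed progression are already cut off by 9.4.1.2. It follows four completed combination cycles, so it is too late to affect 12-week DCR. Whether a second course belongs to the regimen's effect is a choice of estimand.

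**Weight.** DCR is secondary, and section 9.1 makes all analyses descriptive. That lowers the stakes but does not remove the inconsistency.

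**Conclusion.** The concern holds for DCR on the plain wording: a PR or SD first seen on another drug counts as disease control for the study arm, although the ORR rule rejects the same PR. The bias is upward and worth 10, 5 or 2.5 points per affected patient at n = 10, 20 or 40.

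The total size is unknown. One might try to derive it from the figure of about 15% stopping for an AE on durvalumab + tremelimumab in Appendix A 2.7.2.3 (0.15 × 40 = 6 patients). That figure comes from other studies and has no time limit, whereas DCR is affected only by patients who stop and switch before about week 12. The share who switch before progression, and their outcome on the next drug, would both have to be assumed. It does not give a usable estimate.

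The two gaps in the ORR exception are secondary. They rest on a literal reading and call for clarification. Ignoring later therapy for PFS is a deliberate, stated choice and is not criticised here.

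**What to change.** 1. In 9.4.1.1, limit the rule that later anticancer therapy is disregarded to PFS and to the end date of DoR, which follows PFS.
2. In 9.4.1.3, base DCR only on assessments before the start of the first subsequent anticancer therapy. A patient who switches before meeting the DCR criterion counts as not controlled.
3. In 9.4.1.2, reword the ORR exception so that both the initial and the confirmatory scan must precede subsequent therapy, and state that it also applies after an unconfirmed PD. Use the same wording for the modified-RECIST analyses.
4. Add no cut at Arm A retreatment.

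The cost is protocol and SAP wording plus one programming rule. Start dates of subsequent therapy are expressly collected in Arms A and C. Arm B records subsequent therapy in the eCRF, and the form should be checked to confirm that it holds the start date. The reported DCR may be slightly lower, and possibly ORR, since a PR on study drug confirmed only after a switch would no longer count. If that loss matters, such patients can be listed separately.
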